10.6.1 Missing Pain Scores for the Average Scores from BPI-DPN

The means of the Average Daily Pain Scores (Question 5 from the BPI-DPN) for a visit will be considered as missing if fewer than 5 of 7 days of BPI-DPN eDiary entries are provided. Any missing mean pain score of ADPS will be imputed using the methods described below.

Multiple Imputation (MI) method:

- Step 1: Intermittent missing values will first be imputed by treatment group using the Markov Chain Monte Carlo (MCMC) method, resulting in data with a monotone pattern.
- Step 2: Multiple imputation by treatment group using linear mixed model regression with factors of baseline pain score, baseline HbA1c, gender, and age at informed consent (Study VMDN-003-2) will be applied to the data obtained from the MCMC step. The imputed score will be rounded to the first decimal point.

The entire procedure will be repeated 10 times, and 10 complete datasets will be used for the analysis.

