- 7. Urine Drug Analysis includes amphetamines (methamphetamine), barbiturates, benzodiazepines, buprenorphine, cannabinoid (THC), cocaine, oxycodone, methadone, opiates, phencyclidine (PCP), tricyclics (TCA), and ethyl alcohol. Cannabinoid detection is not an exclusion criterion but may be used in exploratory analyses. The urine drug analyses will be conducted on Days 270, 300, and 365/ET. Drug analyses will be performed by the central laboratory.
- **8. HbA1c** levels will be measured on Day 365/ET.
- 9. Concomitant Medications and Procedures: All medications or vaccines, including over-the-counter or prescription medicines, vitamins, herbal supplements, and procedures that the Participant receives will be recorded on Days 270, 300, and 365/ET. For each medication, treatment, or procedure, the following information will be collected: Medication trade or generic name or type of procedure, indication, start date, stop date or ongoing, dose, units, frequency, and route.
- Accurate Pain Reporting (APR): The Accurate Pain Reporting training will be conducted on Days 270, 300, and 365/ET.
 - **Placebo Response Reduction (PRR):** The Placebo Response Reduction training will be conducted on Days 270, 300, and 365/ET.
- 11. Brief Pain Inventory (BPI-DPN) Full Questionnaire will be administered through the ePRO daily starting at 7 days prior to Day 270 and Day 365/ET. The mean of the Average Daily Pain Scores (ADPSs, used for the primary endpoint) is the mean from a minimum of 5 ADPSs recorded in the 7 days prior to the Days 270 and 365/ET Visits. If the ePRO contains fewer than 5 daily entries over the 7 days prior to the Day 270 and Day 365/ET Visits, the visit must be rescheduled (up to 3 days later) so that the Participant can record 5 daily entries over the 7 days.
- **12. Brief Pain Inventory (BPI) Partial Questionnaire** (questions 3, 5, and 9a from the full questionnaire) will be completed on the ePRO every day that the full BPI is *not* conducted from the Day 180 Visit (VMDN-003-2, Initial Visit for this extension study) to the Day 365/ET Visit.

Version 1.0 15 Final: 11 Feb 2021

- 13. Quality of Life Questionnaires (SF-36, EQ-5D) will be administered on Day 270 and Day 365/ET. The study coordinator will check the questionnaires for completeness. Any omissions or ambiguous answers will be clarified by the Participant prior to leaving the clinic.
- 14. Patient Global Impression of Change (PGIC) will be administered on Days 270 and 365/ET.

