8.2. Efficacy Assessments and Procedures

8.2.1. Brief Pain Inventory for Diabetic Painful Neuropathy

The Brief Pain Inventory for Diabetic Painful Neuropathy (BPI-DPN) assessment tool (Section 10.5, Appendix 5) will be administered through use of an eDiary. The Investigator should ensure that the Participant is provided with instructions and is trained to use the eDiary and to complete the assessment tool properly before data collection begins. The BPI-DPN will be conducted using the Full BPI-DPN questionnaire and the Partial BPI-DPN questionnaire

Scores obtained from the Full BPI-DPN during the 7 days prior to the Day 270 and Day 365/ET Visits will be used to determine ADPSs. The ADPS is the mean of at least 5 daily pain scores recorded in the eDiary. If the eDiary contains fewer than 5 daily entries over the 7 days prior to the Day 270 or the Day 365/ET Visits, the Visit must be rescheduled so that the Participant can record 5 daily entries over the 7 days prior to the rescheduled Visit.

Participants will use the eDiary to rate their Average Daily Pain and Worst Daily Pain included in the Brief BPI-DPN on a daily basis from the Day 180 Visit (Study VMDN-003-2) to the Day 365/ET Visit of this extension study to allow an assessment of the level and duration of pain relief in the active treatment group versus Placebo.

Version 1.0 37 Final: 11 Feb 2021

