9.3.1. Primary Endpoint(s)

As described in Section 3, the primary efficacy endpoint is:

 Change in the means of the ADPSs from the full BPI-DPN from the 7 days prior to the Day 0 Visit (Study VMDN-003-2) to the 7 days prior to the Day 365 Visit in the intent-to-treat (ITT) population.

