9.3.2. Secondary Endpoints

The secondary efficacy endpoints include the following:

- Change in the means of the Worst Pain scores from the full BPI-DPN from the 7 days prior to the Day 0 Visit (Study VMDN 003 2) to the 7 days prior to the Day 270 Visit and the 7 days prior to the Day 365 Visit for Engensis compared to Placebo
- Proportion of Responders (≥ 50% reduction in the ADPSs from the full BPI-DPN) from the 7 days prior to the Day 0 Visit (Study VMDN-003-2) to the 7 days prior to the Day 270 Visit and the 7 days prior to the Day 365 Visit for Engensis compared to Placebo

Secondary safety endpoints include:

- Incidence of TEAEs and TESAEs for Engensis compared to Placebo
- Incidence of clinically significant laboratory values for Engensis compared to Placebo

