9.3.3. Exploratory Efficacy Endpoints

Exploratory efficacy endpoints include:

- Patient Global Impression of Change (PGIC) on Day 270 and Day 365 for Engensis compared to Placebo
- Proportion of Responders (≥ 50% reduction in the ADPSs from the full BPI-DPN) during the 7 days prior to the Day 270 Visit and the 7 days prior to the Day 365 Visit who were Responders on Day 104 (final injection visit in Study VMDN 003 2) for Engensis compared to Placebo
- Change in the BST from the Day 0 Visit (Study VMDN 003-2) to Day 270 and to Day 365 Visit for Engensis compared to Placebo

Version 1.0 48 Final: 11 Feb 2021

 Proportion of Responders (≥ 20, 30, 40, 60, and 70% reduction in the ADPSs from the full BPI-DPN) from the 7 days prior to the Day 0 Visit (Study VMDN 003-2) to the 7 days prior to the Day 270 Visit and the 7 days prior to the Day 365 Visit for Engensis compared to Placebo

- Change in the means of the ADPSs from the full BPI-DPN from the 7 days prior to the Day 0 Visit (Study VMDN-003-2) to the 7 days prior to the Day 270 Visit for Engensis compared to Placebo
- Changes in the severity scores (from the full BPI-DPN) from the 7 days prior to the Day 0 Visit (Study VMDN-003-2) to 7 days prior to the Day 270 Visit and to 7 days prior to the Day 365 Visit for Engensis compared to Placebo
- Changes in MNSI assessments from the Day 0 Visit (Study VMDN 003 2) to Day 270 and Day 365 for Engensis compared to Placebo
- Changes in the SF-36 from the Day 0 Visit (Study VMDN 003 2) to Day 270 and to Day 365 for Engensis compared to Placebo
- Changes in the EQ-5D from the Day 0 Visit (Study VMDN-003-2) to Day 270 and to Day 365 for Engensis compared to Placebo
- Changes in the means of the daily use of rescue medication from the Day 180 Visit (Study VMDN-003-2) to Day 270 and to Day 365 for Engensis compared to Placebo

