12.5 Efficacy Analyses

12.5.1 Primary Analysis of the Primary Efficacy Endpoint

The primary analysis for comparing the change in mean Average Daily Pain Scores at the Day 365 visit from Baseline between the treatment groups will be analyzed using the MI method for handling the missing data as specified in Section 10.6.1. A linear mixed-effects model for repeated measures (hereinafter, the continuous Repeated Measures Model) will be used to analyze each complete dataset. The model will include treatment, visit (Day 90 and Day 180 from main study, Day 270 and 365 from extension study), treatment-by-visit interaction, and baseline (Study VMDN-003-2) Average Daily Pain Score as a covariate using an unstructured variance-covariance matrix. Then the Proc MIANALYZE procedures will be used to generate the point estimate for the least-squares mean of the treatment difference (Engensis – Placebo)

and the corresponding 95% confidence interval. LSMEANS, differences and p values compared to baseline will be presented for Day 90 and Day 180 visits from the main study, and Day 270 and Day 365 at the extension study.

The SAS code to be used to for the continuous repeated measure model is presented below:

```
proc mixed data=work order=internal method = REML;
class usubjid trtp avisitn;
model chg = trtp avisitn trtp*avisitn base / ddfm=KR;
repeated avisitn /subject = usubjid type = un;
lsmeans trtp trtp*avisitn / pdiff cl;
run;
```

where

USUBJID: subject ID TRTP: treatment

AVISITN: variable representing visits

CHG: change in the Average Daily Pain Score from baseline(Study VMDN-003-2)

BASE: baseline (Study VMDN-003-2) Average Daily Pain Score (continuous variable)

Other variance-covariance structures selected from among compound symmetry, Toeplitz, and autoregressive (1) options will be substituted based on the lowest Akaike information criterion (AIC) if convergence problems arise.

The primary efficacy analysis will be performed for ITT population.

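### When a visit week stays short of five diary entries, its mean is imputed from a model that does not list the daily pain scores recorded in or just before that week; the likely loss is modest and cheap to recover

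*SAP*

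**What the plan says.** **Collection.** Footnote 12 of the Schedule of Activities (Protocol 1.3) describes the partial BPI-DPN by its items: "questions 3, 5, and 9a from the full questionnaire) will be completed on the ePRO every day" on which the full form is not given. Protocol 8.2.1 has average and worst pain rated "on a daily basis from the Day 180 Visit (Study VMDN-003-2) to the Day 365/ET Visit of this extension study", and gives the reason: "to allow an assessment of the level and duration of pain relief in the active treatment group versus Placebo".

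**Use.** The primary endpoint runs "to the 7 days prior to the Day 365 Visit in the intent-to-treat (ITT) population" (Protocol 9.3.1). The secondary pain endpoints run "to the 7 days prior to the Day 270 Visit and the 7 days prior to the Day 365 Visit for Engensis compared to Placebo" (9.3.2). The exploratory list in 9.3.3 adds, among others, the ADPS change "to the 7 days prior to the Day 270 Visit for Engensis compared to Placebo". The primary model in SAP 12.5.1 also takes Day 90 and Day 180 from the main study.

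**Short weeks.** With fewer than five entries the visit must be rescheduled. Footnote 11 of the Schedule of Activities allows up to 3 days; Protocol 8.2.1 gives no limit. If the visit is missed, SAP 10.3 takes the diary for the 7 days up to Day 270 or Day 365. If five entries are still not reached, SAP 10.6.1 applies: the mean "will be considered as missing if fewer than 5 of 7 days of BPI-DPN eDiary entries are provided". It is then imputed by arm in two steps. Step 1 fills intermittent gaps by MCMC. Step 2 is a linear mixed model with baseline pain, baseline HbA1c, gender and age as factors. The procedure is repeated 10 times. SAP 12.5.2.1 carries the same handling over to worst pain.

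**The concern.** A missing Day 365 mean is always at the end of the visit sequence (Days 90, 180, 270, 365), so it is not intermittent and falls to Step 2. The factors listed there contain nothing about the participant's pain near Day 365, although the diary may hold one to four scores from that very week and two weeks of scores immediately before it. The same applies to a participant who stops the diary between Day 270 and Day 365: the scores recorded up to stopping are not listed as predictors. At stake is precision at the primary visit. Pain shortly before the window is also likely to be related to why entries stop, so leaving it out makes the missing-at-random assumption harder to defend.

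**Working it through.** The documents give no sample size, SD, correlation, dropout or diary compliance, so there is no plan figure to reproduce. Every SD, correlation and compliance rate below is an assumption.

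**1. Days collected and days used.** 365 − 180 = 185 days. The listed pain endpoints use 2 × 7 = 14 of them in the extension: 14/185 = 7.6%.

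**2. How often a week is short.** Entries in a week are taken as Binomial(7, p), with p the daily compliance. Rescheduling is simulated as the best rolling 7-day window over up to 3 later days.

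| Daily compliance p | 1–4 entries, nominal week | Fewer than 5 after rescheduling |
|---|---|---|
| 90% | 2.6% | 0.6% |
| 80% | 14.8% | 5.8% |
| 70% | 35.3% | 19.1% |

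Rescheduling removes roughly 45–75% of failed weeks. A residual share f of 5–15% corresponds to compliance between about 80% and a little over 70%.

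**3. What a partial week is worth.** The error SD of a k-day mean, as a proxy for the 7-day mean, is sd_w × √[(1/k)(1 − k/7)], where sd_w is the day-to-day SD within a week. With sd_w 0.75–1.5:
- 4 entries: 0.25–0.49
- 3 entries: 0.33–0.65
- 2 entries: 0.45–0.90
- 1 entry: 0.69–1.39

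The residual SD of imputation is SD × √(1 − r²). With SD 1.5–2.5 and r 0.5–0.8 it is 0.90–2.17. Two to four entries match or beat imputation throughout this range. A single entry need not (1.39 against 0.90 at SD 1.5, r 0.8).

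**4. Effect on the Day 365 mean.** Take SD 2.0, r 0.5–0.7, sd_w 1.0–1.5, and data missing at random.
- Imputed: relative variance = (1 − r²)/(1 − f) + r².
- Entries kept: relative variance = 1 + f × ē/SD², where ē is the mean over k = 1 to 4 of sd_w²(1/k − 1/7). This is 0.378 at sd_w 1.0 and 0.850 at sd_w 1.5.
- Example, f = 10%, r = 0.5, sd_w = 1.0: 0.75/0.9 + 0.25 = 1.083, against 1 + 0.1 × 0.378/4 = 1.009. Reduction: 1 − 1.009/1.083 = 6.8%.

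| f | Fall in variance | Fall in SE |
|---|---|---|
| 5% | 1.6–3.3% | 0.8–1.7% |
| 10% | 3.4–6.8% | 1.7–3.5% |
| 15% | 5.3–10.4% | 2.7–5.3% |

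The SE column is 1 − √(1 − fall in variance).

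**5. If imputation also uses earlier visit means.** Suppose a share s of daily variance is stable between persons (50–80%) and the rest has day-to-day autocorrelation 0.5. The within-week average of that autocorrelation over 7 days is 0.348, so distant weeks correlate ρ = s/[s + 0.348(1 − s)] = 0.74–0.92. Day 270 alone explains ρ² = 55–85% of the Day 365 week. Days 90, 180 and 270 together explain 3ρ²/(1 + 2ρ) = 67–89%. Putting r² = 0.67 into step 4 at f = 10% gives 0.33/0.9 + 0.67 = 1.037, and a reduction of 1.5–2.6% in place of 3.4–6.8%.

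**6. What the pre-window fortnight adds to those visits.** Under the same model, adding the mean of the 14 days before the window raises R² from 66.5% to 70.3% (s = 50%) and from 89.4% to 90.7% (s = 80%), a gain of 1 to 4 points. If pain also drifts slowly, the gain is much larger. With 50% of variance stable, 30% drifting with day-to-day correlation 0.98 and 20% at 0.5, R² goes from 49% to 81%. These are best-linear-predictor values, c′C⁻¹c/v, from the covariances of the window means.

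**The case against.** The plan has real safeguards. Weeks with five or six entries are used as observed, rescheduling rescues many short weeks, and SAP 10.3 recovers diary data when a visit is missed. A reader might infer that every incomplete week is discarded; the documents do not support that. The safeguards shrink the problem without removing it: neither rescheduling nor SAP 10.3 relaxes the 5-of-7 rule, so a week that is still short goes to imputation.

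A reader might also infer that imputation knows only baseline. The text does not settle this. Step 2 is a mixed model applied to the multi-visit data from Step 1 and could borrow from Days 90, 180 and 270, although no such term is listed. If it does, the gain falls as in step 5 of the working, and the fortnight before the window adds little unless pain drifts. This part of the objection stands, and it limits the size of the point.

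Third, a reader might infer that some 171 diary days (185 − 14) serve no planned analysis. That cannot be established. The SAP's exploratory objectives are redacted, and the section on exploratory efficacy endpoints (12.5.4 in its contents list) is not legible. Protocol 9.3 calls itself a summary. An analysis of duration could be there.

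Finally, a Day 365 landmark is a legitimate durability endpoint. A period average may have a smaller SE, but for a different quantity, so its absence is not a loss of precision at Day 365.

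**Conclusion.** The point holds in a limited form. When a visit week remains below five entries after the permitted remedies, SAP 10.6.1 imputes its mean without listing the scores recorded that week or just before it. Under assumed values (5–15% of weeks with one to four entries, SD 2.0, within-week SD 1.0–1.5, r 0.5–0.7, missing at random) the avoidable variance at Day 365 is about 2–10%, or roughly 1–5% of the SE. It is smaller if earlier visit means already inform the imputation. These figures cover weeks with one to four entries only. The value of pre-window scores for weeks with no entries is not included and depends on how far pain drifts after Day 270. The documents do not support a claim that the primary test is invalid, that much power is lost, or that a single diary entry is precise. The change is worth making because the data are already collected.

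**What to change.** Keep the 5-of-7 definition of an observed score, the primary model and the Day 365 estimand. Amend SAP 10.6.1 before database lock and unmasking:

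1. For each of the Day 270 and Day 365 visit means, add as an auxiliary predictor the mean Question 5 score over the 14 days before that visit's 7-day window, itself imputed when absent. Use Question 3 for worst pain.
2. For weeks with one to four entries, impute the missing days at day level, given the recorded in-window days, the pre-window mean and earlier visit means. Then average to the week mean. Do not enter the partial-week mean as a regression predictor: participants with an observed score have five to seven entries, so for them that predictor is either undefined or identical to the outcome.
3. Optionally, unless the redacted exploratory section already has one, add a supportive repeated-measures analysis of weekly mean ADPS over Weeks 27–52. Label it as a period average and not the Day 365 estimand. It would serve the purpose that Protocol 8.2.1 gives for daily recording.

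One limit should be stated. With a Day 365 window of Days 359–365, the preceding fortnight is Days 345–358. A participant who stops the diary before then has that predictor imputed and gains little from item 1; item 3 would still use the earlier weeks.

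The cost is extra programming and a slightly more complex imputation model. No new data are needed.

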9.0 Population Sets

9.1 Intent-to-Treat (ITT) Population

This subset includes all enrolled Participants in this study who start this extension study at the Day 180 Visit (Study VMDN-003-2). Participants in the ITT population will be analyzed according to original treatment assignment in Study VMDN-003-2, regardless of actual treatment received. The primary analyses of the primary and secondary efficacy endpoints will be based on this ITT population.

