12.5.1.1 Sensitivity Analyses

The primary endpoint will be also analyzed for mITT and PP using the same continuous Repeated Measure Model described in [Section 12.5.1](#).

In addition, there will be a sensitivity analysis accounting for the individual pain scores influenced by the protocol-prohibited concomitant medications. In this analysis, the pain scores after receiving protocol-prohibited concomitant medication will be replaced with the baseline value only if a prohibited medication was used during the 10 days prior to Day 90 visit, Day 180 visit, Day 270 visit or Day 365 visit.

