12.5.3 Subgroup Analysis of Primary and Secondary Efficacy Endpoints

The subgroup analysis for the primary and secondary endpoints will be performed for the following factors:

- Baseline pain score of main study
- Baseline HbA1c of main study (< and ≥ median of main study)
- Gender (male and female)
- Age at informed consent (Study VMDN-003-2) (<65 years and ≥ 65 years)

For each subgroup of the ITT population, the primary and secondary endpoints will be summarized by treatment group and visit using descriptive statistics (n, mean, median, standard deviation, minimum, and maximum for the continuous variable and frequency and percentage for the categorical variable). Both types of descriptive summaries are also provided for the subgroups of study center and protocol version.

Participants will be assigned to a protocol version based on their randomization date and the date of Institutional Review Board (IRB) approval at their site.

The main analysis method described above for the primary and secondary endpoints will be used to analyze the treatment effect within each subgroup. Additionally, the possible treatment-by-subgroup interaction will be tested for each subgroup variable as follows:

- The interaction term for the subgroup variable and treatment group will be included in the analysis model. If the p-value of the interaction term is ≥ 0.05 , the treatment-by-subgroup interaction will be considered not statistically significant.

[REDACTED]

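### The primary model adjusts for baseline pain only, in a set formed after randomisation; an analysis that also adjusts for baseline HbA1c, gender and age, which the SAP already uses elsewhere, should be pre-specified.

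*SAP*

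**What the plan says.** **Imputation.** SAP 10.6.1, Step 2, specifies "Multiple imputation by treatment group using linear mixed model regression". The predictors in that step are listed next: "with factors of baseline pain score, baseline HbA1c, gender, and age at informed consent (Study VMDN-003-2". Only missing mean pain scores are imputed.

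**Primary model.** SAP 12.5.1 describes treatment, visit, "treatment-by-visit interaction, and baseline (Study VMDN-003-2) Average Daily Pain Score as a covariate using an unstructured variance-covariance matrix". The SAS statement agrees: "model chg = trtp avisitn trtp*avisitn base / ddfm=KR". HbA1c, gender and age appear in neither. SAP 12.5.2.1 applies the same method to worst pain. (It cites a Section 8.4.1 that the SAP does not contain; 12.5.1 is evidently meant.)

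**Sensitivity analyses.** SAP 12.5.1.1: "The primary endpoint will be also analyzed for mITT and PP using the same continuous Repeated Measure Model". The other sensitivity analysis replaces scores affected by prohibited medication and adds no covariate.

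**Subgroups.** SAP 12.5.3 lists baseline pain, "Baseline HbA1c of main study (< and ≥ median of main study"), gender and age. For each of these, "The interaction term for the subgroup variable and treatment group will be included in the analysis model".

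**Analysis set.** SAP 9.1 defines the ITT population: "This subset includes all enrolled Participants in this study who start this extension study at the Day 180 Visit". Under SAP 8.1, those are participants who complete Day 180 and consent to the extension.

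**The concern.** The plan already needs three further main-study baseline variables, yet they play no part in the primary comparison. Within imputation they affect only the filled-in scores, so observed scores are never adjusted for them.

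This matters more here than in an ordinary randomised comparison. Entry to the extension is decided about six months after treatment starts, by completion and consent, and either could differ by arm. Randomisation then no longer secures balance on age, gender or glycaemic control among those analysed. Any imbalance in a prognostic variable passes into the Day 365 difference. If it is noticed only after unmasking, an adjusted analysis would be post hoc and open to challenge.

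**Working it through.** **1. Models side by side.**

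| Variable | Imputation (10.6.1) | Primary model (12.5.1) | Subgroups (12.5.3) |
|---|---|---|---|
| Baseline pain | yes | yes | yes |
| Baseline HbA1c | yes | no | yes |
| Gender | yes | no | yes |
| Age | yes | no | yes |

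The mITT and PP analyses reuse the primary model in sets selected further on Day 365 diary data. The subgroup models give within-subgroup effects and interaction tests, not an overall adjusted estimate.

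**2. Inputs.** The SAP and protocol give no sample size, SD, power or R-squared for the extension (SAP 8.1; protocol 9.1 defers to the main study), so there is no planned figure to reproduce. Everything below is illustrative. R² means the assumed partial R-squared of the three covariates jointly, given baseline pain.

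**3. Precision.** Gain factor: sqrt(1 − R²). Approximate cost of three further coefficients: sqrt((N − 5)/(N − 8)). At an assumed N = 120 the cost is sqrt(115/112) = 1.0133, and break-even R² is 3/115 = 0.026.

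| Assumed R² | sqrt(1 − R²) | × 1.0133 | Net change in SE |
|---|---|---|---|
| 0 | 1.0000 | 1.0133 | +1.3% |
| 0.02 | 0.9899 | 1.0031 | +0.3% |
| 0.026 | 0.9869 | 1.0000 | about 0 |
| 0.05 | 0.9747 | 0.9876 | −1.2% |
| 0.10 | 0.9487 | 0.9613 | −3.9% |

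At N = 100 the cost is 1.6% and break-even R² about 0.03; at N = 150 they are 1.0% and 0.02.

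**4. Imbalance from selective entry.** This was simulated with a single-visit ANCOVA: 4000 runs per setting, 150 randomised, no true effect, residual SD 1. The three covariates were independent and equally predictive. Baseline log-odds of entry were 1.4, so about 80% enter (1/(1 + e^−1.4) = 0.80), or roughly 120. Where entry depended on a factor, the slope was 0.8 on the log-odds scale. Bias is in residual SD units; three values are for R² = 0.02, 0.05 and 0.10.

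| Entry depends on | Bias, current covariates | Bias, three added |
|---|---|---|
| nothing | about 0 | about 0 |
| the three covariates, in opposite directions by arm | 0.05, 0.08, 0.10 | about 0 |
| an unmeasured factor, in opposite directions by arm | about 0.19 | about 0.19 |
| Day 180 pain, in one arm only | about 0.13 | 0.12, 0.12, 0.11 |

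For an assumed residual SD of 2.0 to 2.5 points, the second row runs from 0.047 × 2.0 = 0.09 to 0.103 × 2.5 = 0.26 pain points before adjustment. The selection strength is assumed; nothing in the documents shows that entry works this way.

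**5. Chance imbalance.** This is not a separate benefit. Its variation is already in the confidence interval, and removing it is the precision gain of step 3.

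**The case against.** The strongest reply is that nothing is wrong. The model already adjusts for baseline pain, text and code agree, and further covariates are a design choice. Much of that stands. A reader might infer from the table in step 1 that the imputation and analysis models conflict; they do not, because a richer imputation model is accepted practice. Nor does the SAP call these variables prognostic. Imputation variables may be chosen because they relate to missingness, and subgroup factors because they may modify the effect.

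A reader might also infer that adjustment buys precision at no cost. The documents do not support that: no R-squared is given, and below break-even the standard error rises slightly.

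A third tempting inference is that adjustment repairs the post-randomisation set. It does not. Step 4 shows little help when entry depends on Day 180 pain and none for an unmeasured factor.

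Three practical objections also stand. Imputation is by arm, so adding common covariate effects does not make the two models identical. Main effects held constant over four visits remove the Day 365 imbalance in full only if those effects are constant. PROC MIXED drops records with a missing covariate, and the SAP has no rule for missing baseline HbA1c.

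Partial cover exists: SAP 12.2 tabulates age and sex by arm, and the subgroup tables would show the HbA1c split. That makes an imbalance visible but leaves the primary estimate unchanged. The gap that remains is the lack of any pre-specified overall estimate adjusted for these variables.

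**Conclusion.** The point holds as a low-cost improvement, not as an error. The primary model omits three baseline variables that the plan already requires, in a set where randomisation does not guarantee balance, and no planned analysis fills the gap.

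The firm benefit is removal of measured imbalance in HbA1c, gender and age. The precision effect is modest and could go either way: from about +1.3% to −3.9% in standard error over an assumed partial R-squared of 0 to 0.10 at an assumed N of 120. The bias figures rest on assumed selection strength and residual SD and show what adjustment can and cannot do; they do not estimate bias in this trial. Selection linked to Day 180 response or to unmeasured factors is a separate matter that this change leaves essentially untouched.

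**What to change.** Before database lock and unmasking, amend SAP 12.5.1 and 12.5.2.1:

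- Add main-study baseline HbA1c (continuous), gender (in the CLASS statement) and age (continuous) as fixed covariates, preferably with covariate-by-visit terms, or at least so that the Day 365 contrast is adjusted: `class usubjid trtp avisitn sex; model chg = trtp avisitn trtp*avisitn base hba1c_bl sex age hba1c_bl*avisitn sex*avisitn age*avisitn / ddfm=KR;`
- State a simple rule for missing baseline HbA1c, for example the median pooled over arms, so that no participant is dropped.
- Keep the current model as a supportive analysis.

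If the sponsor prefers to leave the primary model alone, the minimum is to pre-specify the adjusted model as a sensitivity analysis in 12.5.1.1.

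Cost: SAP wording, a few model terms and no new data. Main effects use three degrees of freedom; with visit terms there are 3 × 4 = 12 coefficients, three per visit. If the covariates are not prognostic, the standard error rises by about 1%.
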